Each local principal investigator will have ongoing support from an assigned EAGLE Coordinator with at least weekly teleconference or email contact. As the study proceeds EAGLE Coordinators will tailor the content of these weekly contacts to the specific study processes that are relevant at that time.

All training has been CPD-accredited (3 points) by the Royal College of Surgeons of England.

Site training is mandatory and completion of each module by the relevant staff is a prerequisite to site opening to recruitment. The monitoring of completion of training will be undertaken by staff at the EAGLE Study Office.

Prior to opening, all participating local Principal Investigators will sign an Investigator's Agreement with the University of Birmingham to document acceptance of the responsibilities of the PI at the site.

Monitoring

Due to the nature of EAGLE, monitoring will be employed to ensure the credibility of the data. Monitoring will be undertaken centrally and will include, but will not be limited to, monitoring of: protocol adherence; patient selection and minimisation of selection bias; review of data relating to the primary and secondary outcomes. Monitoring will be via data validation and range checks built into the REDCap database used to collect and manage the data; statistical monitoring techniques will be used to compare data from different sites to identify sites that may warrant further investigation, site monitoring and/or support and training. Review by the study oversight committees (SSC, DMOC, SMG) will also include the review of completion of primary and secondary outcomes, adherence to protocol, and selection bias.

EAGLE study staff from UoB will be in regular contact with the site research teams to check on progress and address any queries that they may have.

The EAGLE Data Management Committee will check submitted CRFs from the participating hospitals for compliance with the protocol, data consistency and missing data. They will send participating hospitals data queries for missing data or clarification of inconsistencies or discrepancies.

Data validation

Validation of case ascertainment (the proportion of eligible cases that were included within the EAGLE study) will be undertaken in a random sample of 10% of centres. In those centres data validation will be led by the Theatre Nurse PI. They will review theatre logbooks to is identify all eligible patients who were operated during the centre's data collection window. The Theatre Nurse PI will confirm these patients' eligibility through consultation with an independent surgeon who has not been involved in the initial data collection at that site. The total number of eligible cases at each site will be submitted to the EAGLE Coordinating Office. The total for eligible cases and cases actually submitted to REDCap will be pooled across centres participating in the validation exercise, and the case ascertainment rate will be calculated.

STUDY ORGANISATIONAL STRUCTURE

The EAGLE Study Office (at the University of Birmingham)

The coordinating centre for the EAGLE study is based at the University of Birmingham through the Birmingham Surgical Trials Consortium (BiSTC).

Each site will appoint a local Principal Investigator (PI) who will take responsibility for the study at site. This will be a consultant (attending) surgeon who is responsible for the overall conduct of the study. In addition, they will recruit three co-principal investigators; this will usually include one surgical trainee, one anaesthetic and one theatre nurse. Each site will be mentored by a member of the Eagle Study Management team, who will provide guidance, oversight and support directly to that site on behalf of the SMG.

Sponsor

The University of Birmingham is the Sponsor of the EAGLE study in all collaborating countries. Sponsorship will be provided by the University of Birmingham upon signing of the Study Agreement with each site.

EAGLE Study Management Group

The EAGLE Study Management Group (SMG) includes those individuals responsible for the day-to-day management of the study. This will include the Chief Investigator, EAGLE operations staff, statisticians, and lead clinicians. The group will meet every six weeks to review ongoing progress. The role of the SMG is to monitor all aspects of the conduct and progress of the study, ensure that the protocol is adhered to and take appropriate action to safeguard the quality of the study itself.

EAGLE Operations Committee

The EAGLE Operations Committee is chaired by the Chief Investigator. It includes the surgical coordinators responsible for the delivery of the study at sites and EAGLE operations staff.

The group will initially meet on a weekly basis at the start of the study and then two-weekly or monthly as the study progresses, dependent on the needs of the project. The role of the operations group is to recruit investigators and hospitals to the study, and to support study set-up at individual hospitals. The Operations Committee will have weekly contact with all participating centres either by teleconferencing or email to ensure adherence to the study protocol. In view of the large size of the study, the Operations Committee will be supported by a wider pool of EAGLE

Coordinators who will act as an interface between local Principal Investigators and the Operations Committee.

EAGLE Data Committee

The EAGLE Data Committee includes the study statistician and EAGLE operations staff. Access to study databases is restricted to the members of the Data Committee. The Data Committee will liaise closely with the Operations Committee to manage and monitor database access.

Study Steering Committee

The remit of the Study Steering Committee (SSC) is to provide overall supervision of the study and ensure that it is being conducted in accordance with the principles of Good Clinical Practice and other relevant regulations.

The SSC will meet face-to-face or via teleconferencing every three months, or more often if required.

The specific tasks of the SSC are:

- To approve and sign off the study protocol and any protocol amendments.
- To resolve problems brought to it by the EAGLE study management team
- To provide advice to the investigators on all aspects of the study.
- To review recommendations from the DMOC, and help with the decision-making that follows on from the recommendations of the DMOC.

Data Monitoring Oversight Committee

The DMOC is scheduled to meet prior to the study commencing every three months thereafter until the study closes to recruitment. Additional meetings may be called if recruitment is much faster than anticipated and the DMOC may, at their discretion, request to meet more frequently or continue to meet following completion of recruitment. An emergency meeting may also be convened if required.

The DMOC will review data completeness, recruitment per-site, recruitment overall, and protocol deviations. The DMOC will make recommendations to the SSC

Finance

EAGLE is an investigator-initiated and investigator-led study. The EAGLE online training packages have been developed with an unrestricted educational grant from Ethicon. The overall funding for study conduct has been provided by the European Society of Coloproctology.

CONFIDENTIALITY AND DATA PROTECTION

Patient identifiable information will not be collected in this study. All participant data held at the University of Birmingham will be anonymised.

All data collected about participants will be identified using only a unique EAGLE study number. This number will be automatically allocated via REDCap once a new patient record is created in the EAGLE REDCap database.

Any correspondence between the EAGLE study office and hospital sites will use the EAGLE study number only.

The linkage between REDCap study ID and participants will be maintained in strict confidence at participating sites. This data will not be submitted to the EAGLE study office and will not be sent outside of the participating site.

Confidentiality of all participant's data will be maintained and there will be no disclosure of information by which participants may be identified to any third party other than those directly involved in the treatment of the participant.

INSURANCE AND INDEMNITY

The University of Birmingham has in place Clinical Trials indemnity coverage for this study which provides cover to the University for harm which comes about through the University's, or its staff's, negligence in relation to the design or management of the study.

The risk of the trial is no greater than the risk of the standard clinical care. Responsibility for the participants at Sites remains with the organisation responsible for the Clinical Site and it is therefore indemnified through their normal arrangements.

AUTHORSHIP

The output from this research will be published under a single corporate authorship group: "European Society of Coloproctology Safe-anastomosis Collaboration". The following roles will be

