 - All patients undergoing right colectomy are eligible, including those who do not have an anastomosis and are defunctioned by a proximal stoma.
- Procedures for any pathology, via any operative approach (open, laparoscopic, robotic or converted) are eligible.
- Elective (surgery on a planned admission), expedited, and emergency (surgery on an unplanned admission) procedures are eligible.

Patient exclusion criteria

- Patients undergoing more than one gastrointestinal anastomosis during the same operation.
- In Crohn's disease, additional upstream strictureoplasty or resection/anastomosis to treat disease or strictures at the same operation.
- Simultaneous right colectomy and hyperthermic intraperitoneal chemotherapy (HIPEC) and/or cytoreductive surgery.
- Each individual patient should only be included in EAGLE once. Following the index procedure that is included in EAGLE, patients undergoing additional procedures within the study window should not be included for a second time.

Selection bias

Selection bias will be closely monitored by the Study Management Group. EAGLE coordinators will regularly liaise with site Principal Investigators to ensure that all eligible patients are entered into the EAGLE study. Recruitment rates will be monitored across individual sites and clarification will be sought in case of a drop in recruitment that might indicate that eligible patients were not included. An independent validation process will monitor case ascertainment (see *Monitoring* and *Data Validation*, page 24-25).

PATIENT IDENTIFICATION

Each participating country and hospital will decide how best to identify eligible patients.

Patients can be identified either before, during, or after surgery. As guidance, it is anticipated that patients may be identified from any of the following settings, but that this should preferentially be performed pre-operatively:

- Pre-operatively: surgical outpatient clinics (e.g. when the patient is being booked for elective surgery); planned theatre lists (e.g. at the time of admission for surgery); emergency surgical admissions (e.g. at the time that a decision to operate is made)
- Intra-operatively: by the operating surgical teams during the in-theatre Safe-anastomosis checklist, once the procedure eligibility has been confirmed.
- Post-operatively but before discharge: by either the operating surgeon or by review from the research team.

Patients will be identified by a suitable person who may include:

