The study intervention will be introduced at a specific timepoint determined by the randomisation sequence. Sites will not be exposed to the study intervention before their allocated timing and this will be ensured by time-locked password access to QII materials.

Intervention details

The EAGLE Safe-anastomosis Quality Improvement Intervention (QII) is a behavioural change intervention composed of three parts:

1. Routine patient-level stratification of risk of anastomotic leak

Calculation of a preoperative risk for each patient undergoing right colectomy or ileocaecal resection using the anastomoticleak.com risk calculator. This includes six factors: Gender; Body Mass Index >30; Anticoagulant use; Intraoperative complication; Serum protein level; Hospital size. Investigators will be trained and encouraged to preoperatively calculate the risk with or without an intraoperative complication. This risk estimate will be used to inform shared decision

making with the patient preoperatively, and will be reviewed in light of intraoperative events as part of the ECSP Safe-anastomosis Checklist.

2. ESCP Safe-anastomosis Checklist

The ESCP Safe-anastomosis Checklist will be implemented in-theatre, immediately prior to the time of formation of an anastomosis or formation of a stoma; this can be before or after transection of the bowel. The checklist should be completed by an unscrubbed member of the theatre team in partnership with the operating surgeon(s), other members of the surgical team, the scrub nurse(s), anaesthetist(s) and operating department practitioner(s).

The Safe-anastomosis checklist (Appendix 1) consists of:

- (1) Review of any concerns from the anaesthetist, including the anaesthetic risk, haemodynamic instability, vasopressors, blood transfusion, operating time greater than 4 hours, or blood loss greater than 100mls;
- (2) Review of any concerns from the surgical team, including the surgeon, scrub staff and operating theatre practitioners. A consensus decision for primary anastomosis (with or without defunctioning enterostomy) or defunctioning enterostomy without anastomosis will be then made by the operating surgeon.
- (3) If the consensus decision is to proceed with anastomosis; planning equipment, anastomotic configuration, and delivery of an agreed anastomotic technique, including intra-operative checking of anastomosis integrity.

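### Because the exclusion counts anastomoses actually made, patients with a second bowel resection can enter differentially after the intervention; the likely bias is small and confined to secondary and process outcomes

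*Protocol*

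**What the plan says.** Four parts of the Protocol bear on this.

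- **Eligibility, exclusion criteria.** One criterion removes "Patients undergoing more than one gastrointestinal anastomosis during the same operation". A separate one covers Crohn's disease with "additional upstream strictureoplasty or resection/anastomosis to treat disease or strictures at the same operation".
- **Eligibility, inclusion criteria.** "All patients undergoing right colectomy are eligible, including those who do not have an anastomosis and are defunctioned by a proximal stoma". Making no anastomosis is therefore no bar to entry.
- **Intervention details, item 2 (checklist).** The checklist is run just before an anastomosis or a stoma is formed. It leads to this step: "A consensus decision for primary anastomosis (with or without defunctioning enterostomy) or defunctioning enterostomy without anastomosis will be then made by the operating surgeon".
- **Secondary process objectives.** A change in anastomotic practice is to be evaluated by following the proportions of patients with an anastomosis, with an anastomosis plus defunctioning stoma, and with a defunctioning stoma.

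The Blinding section adds that neither the surgeon nor the outcome assessor can be blinded. Under the outcome measures, the primary outcome and reoperation for leak are counted in patients with a primary anastomosis. All other secondary outcomes are counted in all patients.

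**The concern.** An entry criterion should not depend on something the intervention can change. Here the number of joins is fixed during the operation, after allocation, by staff who know the allocation. The checklist acts on one of those joins.

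Consider a patient without Crohn's disease who needs a right colectomy and a second bowel resection. If both sites are joined, there are two anastomoses and the patient is out. If the ileocolic join is replaced by an ileostomy, at most one anastomosis remains and the patient is in. If the checklist makes the second course more common, patients of this type enter the post-intervention sample while comparable patients in the pre-intervention periods are correctly left out.

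At stake is the comparability of the two samples for the all-patient outcomes: ileostomy without anastomosis, mortality, unplanned critical care, reoperation for any cause, readmission and stay. The process objective on stoma proportions is exposed in the same way. This is separate from the choice of primary denominator, because analysing every included patient would not bring back patients who were never entered.

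**Working it through.** **Does the route exist?** Reading the sections together for a second resection without Crohn's disease:

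| Decision in theatre | Anastomoses | Status under the criteria |
|---|---|---|
| Both sites joined | 2 | Excluded |
| Ileostomy instead of the ileocolic join | 0 or 1 | Eligible |

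Nothing else in the exclusion list removes the second patient unless hyperthermic chemotherapy or cytoreductive surgery is involved. The checklist need not address the second join, because giving up the ileocolic join is enough.

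**Would the safeguards show it?**

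- The selection-bias check looks for a drop in recruitment. This route adds patients.
- Data validation compares submitted with eligible cases in 10% of centres. Both counts use the same criterion, so ascertainment could be complete with the shift still present.
- The case report form (Appendix 2) has no field for the number of anastomoses or for an additional resection.

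**Which outcomes are reached?** A patient with an ileostomy in place of the ileocolic join is outside the primary denominator. Only all-patient outcomes and the stoma proportions are affected.

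**How large?** The protocol gives no figure to reproduce on this point. All inputs below are assumptions:

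- m = share of right colectomies with a second resection: 5% (also 10%).
- d = further share of these diverted to an ileostomy after the intervention: 5%, 10%, 20%.
- Ileostomy rate in other patients: 5%, unchanged by the intervention.

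Shift = [0.05(1 − m) + m·d] / [(1 − m) + m·d] − 0.05

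| m | d | Calculation | Shift (points) |
|---|---|---|---|
| 5% | 5% | 0.0500/0.9525 − 0.05 | +0.25 |
| 5% | 10% | 0.0525/0.9550 − 0.05 | +0.50 |
| 5% | 20% | 0.0575/0.9600 − 0.05 | +0.99 |
| 10% | 5% | 0.0500/0.9050 − 0.05 | +0.52 |
| 10% | 10% | 0.0550/0.9100 − 0.05 | +1.04 |
| 10% | 20% | 0.0650/0.9200 − 0.05 | +2.07 |

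The reference is a population without second resections, which is what the revised criterion would define. Among all right colectomies, second resections included, the same diversions would be a real change of m·d = 0.05 × 0.10 = 0.5 points. The figure is a bias only with respect to the narrower population.

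**How many patients?** The 333 clusters give 111 per sequence. Sequences 1 and 2 each supply one post-intervention period of 10 patients, so 2 × 111 × 10 = 2,220. With m = 5% and d = 10%, the extra patients are 0.005/0.955 = 0.52% of that sample, or about 12. With d = 5% or 20% they number about 6 or 23.

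**Effect on another outcome.** If the extra patients' mortality were 10 points higher (assumption), overall mortality would move by 0.0052 × 10 = 0.05 points.

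**The case against.** The strongest objection is about size and generality. Entry changes only for a patient who has a second resection, is not already removed by another exclusion, and has the ileocolic decision altered by the checklist. The protocol gives no frequency for any of these, and the magnitude depends on assuming no effect elsewhere. Suppose 10% of the other anastomosed patients were diverted too. Their ileostomy rate would go from 5% to 0.05 + 0.95 × 0.10 = 14.5%. The observed rate would be (0.95 × 0.145 + 0.005)/0.955 = 14.95%, a distortion of about 0.45 points on a real change of 9.5. All of this stands and keeps the point minor.

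The criterion also has an evident purpose: with two joins, a leak or collection is hard to attribute to the ileocolic one. A rule based on resection would itself rest on something that may be settled during surgery. Both remarks are fair. However, the revised wording still excludes every two-anastomosis case, and the checklist names the anastomosis-or-stoma decision, not the decision to resect a second segment.

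A reader might infer three stronger claims that the Protocol does not support.

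- *Eligibility cannot be settled in time.* One identification setting is "by the operating surgical teams during the in-theatre Safe-anastomosis checklist, once the procedure eligibility has been confirmed". But that list is guidance, and "Patients can be identified either before, during, or after surgery". Patient Entry asks only that eligibility be confirmed before the form is completed, so the number of joins can be known by then.
- *The two exclusions contradict each other.* They differ in scope. The Crohn's rule concerns upstream disease and strictures and includes strictureoplasty. Its wording is a useful model, but the difference is not an inconsistency.
- *The primary comparison is biased.* That would need the second join, not the ileocolic one, to be given up, and nothing says the checklist aims at it. Even then, assume 1–5% two-anastomosis operations, 2–20% of them switching, and a leak risk of 12–20%. With f the product of the first two and L the leak risk, (0.056 + f·L)/(1 + f) − 0.056 gives 0.001 to 0.14 points, against a target difference of 2.5.

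**Conclusion.** The point holds in a limited form. Entry partly depends on a post-allocation decision that the intervention targets and that unblinded staff make, and the planned checks would not reveal it. Patients without Crohn's disease who have a second resection can therefore enter differentially after the intervention.

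It would go too far to say that the same patient is, as a rule, excluded before and included after. Each patient enters once, so that contrast is counterfactual, and it concerns only patients whose decision actually changes.

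The primary outcome is not affected by this route. The exposure is a probably small bias in all-patient secondary outcomes, chiefly ileostomy without anastomosis, and in the stoma proportions of the process objective. At 5% second resections the ileostomy rate shifts by about 0.25 to 1.0 points, and at 10% by about 0.5 to 2.1. Every input is assumed, including no effect in other patients. The case for acting rests on the low cost of the change more than on the size of the bias.

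**What to change.** Reword the exclusion so that it does not depend on how the bowel ends are managed, for example: *any additional gastrointestinal resection or anastomosis at the same operation, whether the ends are joined or brought out as a stoma*. Apply it identically before and after the intervention. This keeps the purpose of the present criterion and changes one sentence. The cost is the loss of the few patients with a second resection and no more than one anastomosis, whom the protocol now admits.

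If the criterion is to stay, log the right colectomies excluded for two anastomoses in each period and report the counts before and after the intervention. That would show whether exclusions fall after the intervention, but would not remove the effect.
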